Long-term weight loss studies consisting of diet and exercise manipulation have highlighted beneficial effects on inflammation and clinical outcomes in overweight persons both with ^[4] and without OA ^[5], and 3-4 weeks of exercise exposure has been shown to positively influence pain and function in those with symptomatic knee OA^[6]. We hypothesise that by creating a short-term negative energy balance through a combination of caloric restriction and exercise ^[7] that we will be able to reduce inflammation in individuals with knee OA. We also aim to determine if a dietary energy restriction condition can also reduce inflammation. We will examine changes in systemic biomarkers associated with inflammation in those with early-stage knee OA in response to the short-term interventions. We will also assess the impact of the intervention upon self-reported measures of pain/function and performance in functional tests. Importantly, we will be able to determine any of these effects without the confounding factor of substantial weight loss present in longer-term interventions.

As well as tracking symptomatic pain, it is also relevant that we incorporate a range of experiential pain measures. Such measures are used to assess pain sensitisation which is a phenomenon reported in individuals who suffer with knee OA ^[8]. Pain sensitisation in the knee OA population is suggested to be caused by peripheral inflammation at the joint and systemic level altering the way that the central nervous system responds to tactile and noxious stimuli ^[9].

The study will include both male and female participants that fit the eligibility criteria. Participants' activity levels and dietary intake will be monitored for 7 days and each will then be randomised into 1 of 2 intervention groups. Both groups will complete a 4-week observational wash-in period for us to determine the stability of the biomarkers, with participants acting as their own controls. Both intervention groups will then reduce their caloric intake by 5000kcal/week over 4 weeks, and the second intervention group will have the addition of 5 moderate-vigorous intensity exercise sessions (based upon target ratings of perceived exertion) per week for 30 minutes using a cycle ergometer to determine the added effects of exercise.

Systemic biomarkers in Osteoarthritis

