Diet and exercise treatments are widely recommended through clinical guidelines with the aim of improving pain and functional ability [28], and it is well documented that the manipulation of diet and/or exercise, have beneficial effects on systemic inflammation [29, 30], especially in those who are overweight/obese. Despite this, the current scope of research around the effects of diet only and combined diet and exercise treatments on OA biomarkers lacks in both the number of available studies, and the biomarkers assessed in those studies [31]. Additionally, those studies that have induced a negative energy balance through diet and exercise manipulation have been long-term investigations whereas our study is focused on relatively short-term changes. This has the potential benefit of improving systemic inflammation while being relatively independent of the effect of substantial weight change (i.e. loss of >5kg often seen in longer term studies), which is known to be a critical factor that reduces systemic inflammation[32] and can also independently improve pain and functional outcomes.

Purpose of study

The primary aim of the study is to assess changes in the primary clinical biomarker of systemic inflammation (CRP) in individuals with knee osteoarthritis.

We hypothesise that a 4-week lifestyle intervention employing a negative energy balance will decrease systemic CRP concentrations.

Secondary outcome variables –

- Changes in systemic pro- and anti-inflammatory cytokines and chemokines associated with knee OA.
- Changes in fasted markers of metabolic function (glucose, NEFA, triglycerides, total/HDL cholesterol)
- Changes in self-reported functional and pain outcomes
- Changes in functional tests
- Changes in experimental pain measurements

Participants

Eligibility for participation in this research trial will be based on information and measurements gathered at a preliminary screening visit.

We will recruit participants based on the following eligibility criteria:

- Diagnosed with uni -or bi-lateral knee osteoarthritis. Clinically deemed to be appropriate for conservative treatment and not surgical intervention through Virgin Care.
- Male or females with clinically diagnosed and radiographically confirmed knee osteoarthritis. Exclusion of other possible causes of knee pain/arthritis determined based upon clinical reasoning.
- Aged between 45 to 69 years.

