- 1) Potentially eligible patients attending a Health Optimisation clinic for Osteoarthritis (for individuals with a BMI >30 kg/m² or current smokers) as part of services provided by Virgin Care will be provided with study information. These individuals have been previously clinically diagnosed with knee osteoarthritis by a physiotherapist or general practitioner before being referred to the Health Optimisation Clinic. Physiotherapists or exercise instructors delivering these classes will provide study information (Participant Information Sheet) to potentially relevant individuals based upon age, body mass and Oxford Knee Score as described in inclusion criteria above.

As part of this identification process, only the direct care team will interact with the patients to the point at which individuals are provided with study information.

Sample size

A previous intervention conducted in sedentary overweight and obese women using the same energy restriction model for 3 weeks^[7], established an effect size of 1.22 for the change in CRP with dietary energy restriction and vigorous intensity exercise 5 x per week. Using this effect size, an α of 0.05, and a power of 80%, it is estimated that a sample size of 8 would be

required for a two-tailed paired comparison. However, as we would hypothesise that the effect of the diet only intervention would be less, due to the lesser energy restriction and independent impact of exercise training upon CRP, an estimated effect size of 0.85 is proposed. Using an α of 0.05, and a power of 80%, it is estimated that a sample size of 13 would be required for a two-tailed paired t-test. Assuming a dropout rate of ~25%, we would aim to recruit ~16 individuals in each intervention arm. Between-group comparisons will be exploratory in nature, to determine sample sizes of future studies comparing the efficacy of the conditions.

Group allocation/Randomisation

Following screening/baseline measures of those included, participants will be allocated to either intervention group 1 (Diet restriction) or intervention group 2 (Diet restriction + Exercise) by an individual outside of the research team who will have no interaction with participants. To protect against chance imbalance between the two groups, this will be conducted via minimisation accounting for participant sex, age, BMI, and Oxford Knee Score.

Outcome measures

Primary outcome variable

- Change in the primary clinical biomarker of systemic inflammation (CRP).

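### Does testing CRP in each arm at 0.05, with no order or pooled test, double the false-positive risk for the primary hypothesis?

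*Protocol*

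**What the plan says.** The section Purpose of study gives a single directional hypothesis that names no arm: "We hypothesise that a 4-week lifestyle intervention employing a negative energy balance will decrease systemic CRP concentrations". The primary outcome is the change in CRP.

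The opening background text, ahead of the section Systemic biomarkers in Osteoarthritis, is more specific. It first hypothesises an anti-inflammatory effect of caloric restriction combined with exercise, and then adds: "We also aim to determine if a dietary energy restriction condition can also reduce inflammation".

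The Sample size section follows the same sequence. For the combined regimen it cites a previous study that "established an effect size of 1.22 for the change in CRP with dietary energy restriction and vigorous intensity exercise 5 x per week". From that value, with α at 0.05 and 80% power, it arrives at 8 participants, the number "required for a two-tailed paired comparison". For diet only it assumes a smaller effect of 0.85, because the energy restriction is less and the separate effect of training is absent. That gives 13 for a two-tailed paired t-test, again at α 0.05 and 80% power. After an allowance of about 25% for dropout, "we would aim to recruit ~16 individuals in each intervention arm". On the contrast of the arms it says: "Between-group comparisons will be exploratory in nature".

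The Protocol has no statistical analysis section. It names no primary model, decision rule or approach to multiplicity.

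**The concern.** Set beside the sample-size calculation, the general hypothesis appears to have two routes to success. Both arms cut dietary intake by 5000 kcal per week, so both create a negative energy balance. Each is sized for its own test at the full 0.05, and nothing orders or combines the two tests.

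If a positive result in either arm counted as support for the one hypothesis, the error rate for that hypothesis would be about twice the nominal level. If only one arm were significant, the primary question might have no agreed answer, and the split could tempt readers into a between-arm claim that the trial is not sized to make. A single test over both arms would use twice as many participants and would be more powerful than either arm alone.

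**Working it through.** **1. The Protocol's own figures.** For a two-sided paired t-test, power is taken from the noncentral t distribution with n − 1 degrees of freedom and noncentrality d√n.

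- Combined regimen, d = 1.22: n = 7 gives 76.7% and n = 8 gives 84.0%, so 8 is the smallest sufficient number.
- Diet only, d = 0.85: n = 12 gives 76.4% and n = 13 gives 80.3%, so 13 is the smallest sufficient number.

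Both stated numbers reproduce as unadjusted tests at 0.05. The sizing is therefore per arm. That shows how n was chosen. It does not show which test decides the hypothesis in Purpose of study.

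**2. Error rate under each possible rule.** The arms hold different participants, so the two tests are independent.

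| Rule | False-positive rate when neither regimen works |
|---|---|
| Either arm suffices, either direction counts | 1 − 0.95² = 9.75% |
| Either arm suffices, only a decrease counts | 1 − 0.975² = 4.94% |
| Both arms must be significant | 0.05² = 0.25% (at most 5% if one regimen truly works) |
| Each arm is its own claim | 5% per claim |

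Only the first row gives about 10%. It needs an either-arm rule that the Protocol does not contain, and it counts increases in CRP, which would contradict the stated hypothesis.

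**3. One claim or two.** The opening text poses the combined regimen and the diet-only regimen as two questions in sequence. The Sample size section gives each its own effect size and explains why they should differ. On that reading the last row applies, and a split result has an answer: one regimen lowered CRP and the other was not shown to.

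**4. How often a split would occur under the stated effects.** With 13 completers per arm, power is 0.803 for diet only and 0.981 for the combined regimen.

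- Both significant: 0.8031 × 0.9806 = 78.7%.
- At least one significant: 1 − 0.1969 × 0.0194 = 99.6%.
- Exactly one significant: 99.6% − 78.7% = 20.9%.

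Of that 20.9%, 0.9806 × 0.1969 = 19.3 percentage points are cases where only the combined regimen is significant, the pattern to be expected when the assumed effects differ as they do.

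**5. What pooling would add.** With 26 completers and d = 0.85 in both arms, a pooled test has 98.6% power, against 80.3% for diet only. For the general question, however, the fair comparison is the 99.6% for at least one arm, although that rule does not hold two-sided error at 5%.

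A pooled test also cannot say whether diet alone works. Suppose diet only had no effect and the combined regimen had 1.22, with equal standard deviations. The mean effect would be (0 + 1.22)/2 = 0.61, and the pooled test with 24 completers would still be significant about 81% of the time (noncentrality 0.61 × √24 = 2.99, 22 degrees of freedom).

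**The case for a change.** The strongest opposing argument is that the Protocol commits itself to α and n, so this cannot all be deferred. If an SAP split α into 0.025 per arm, diet only would need 16 completers, and 13 would give 69.1% power. The doubling also survives the change of scale: 4.94% for a false decrease compares with 2.5% for one two-sided test in that direction. With 16 recruited and 25% lost, 16 × 0.75 = 12 remain per arm, and the chance of a split result rises to 25%. Finally, the value 0.85 is proposed without a source. If the true effect were 0.60 in each arm (an assumption), each test of 12 would have 47% power, against 80% for a pooled test of 24.

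These numbers are correct, and two points stand. The section Purpose of study does not say which test decides its general hypothesis. A pooled test would also be the more powerful choice if the effects were small and similar in both arms.

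Neither makes the plan wrong. The α split is a problem only if a split is required, and separate claims about two regimens do not require one. The doubling, on either scale, depends on the unstated either-arm rule. Pooling, or testing diet only last in a fixed order, is a trade-off: the order would lower diet-only power with 12 per arm from 76.4% to 0.9696 × 0.7644 = 74.1%. Whether 12 completers per arm are enough is a separate matter of dropout inflation. The risk of an unsupported between-arm claim is met by the Protocol's own statement that such comparisons are exploratory.

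**Conclusion.** The concern does not hold. The Protocol's sample sizes reproduce, and nothing in it states that one significant arm is enough or that a pooled analysis is excluded. The figure of about 10% belongs to one unstated rule. Under the reading best supported by the opening text and the Sample size section, each regimen is a separate claim tested at 0.05, and the error per claim is 5%.

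The choice between separate and pooled testing is one on which reasonable statisticians differ. Under the stated effects with 13 completers per arm, 99.6% power for at least one arm leaves little for pooling to gain on the general question.

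The gap that remains, the rule linking the general hypothesis to a particular test, is missing detail of a kind usually given in an SAP. This conclusion rests on independence of the two arms, on the Protocol's effect sizes of 1.22 and 0.85, and on reading the two regimens as two questions. It would change if an SAP declared that significance in either arm confirms the single hypothesis without adjustment.

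### Sixteen recruits per arm with 25% dropout leave 12 completers, not the 13 required, so the diet-only calculation has about 76% power instead of 80%

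*Protocol*

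**What the plan says.** The Sample size section of the protocol makes two within-arm calculations for the change in CRP, the primary outcome.

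- **Diet plus exercise.** An earlier 3-week study "established an effect size of 1.22 for the change in CRP with dietary energy restriction and vigorous intensity exercise 5 x per week". From this the protocol derives a requirement of 8 for a two-sided paired comparison.
- **Diet only.** A smaller effect is expected, so "an estimated effect size of 0.85 is proposed". At alpha 0.05 and 80% power, "a sample size of 13 would be required for a two-tailed paired t-test".

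The larger requirement, 13, is then carried into one recruitment target for both arms: "Assuming a dropout rate of ~25%, we would aim to recruit ~16 individuals in each intervention arm".

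The comparison between arms is not powered: "Between-group comparisons will be exploratory in nature, to determine sample sizes of future studies comparing the efficacy of the conditions".

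**The concern.** A dropout rate applies to the people recruited, so the number to recruit is the number of completers needed divided by one minus the dropout rate. The target of about 16 does not follow from 13 completers and 25% dropout on that basis. It does match 13 × 1.25 = 16.25, which applies the rate to the completers instead. The protocol gives no inflation formula, so this origin is an inference, and the point does not depend on it.

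At stake is the 80% power claimed for the primary outcome. The within-arm paired test is the only powered analysis, since between-arm comparisons are exploratory. The diet-only arm has the smaller assumed effect and therefore sets the size of the trial. If dropout is as the protocol expects, this arm ends below the protocol's own minimum.

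**Working it through.** **Inputs, all from the protocol's Sample size section:** two-sided alpha 0.05; power 80%; paired t-test within arm; effect size 0.85 (diet only) and 1.22 (diet plus exercise); dropout about 25%; about 16 recruited per arm.

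**Step 1: reproduce the protocol's base figures.** Exact power of a two-sided paired t-test with n pairs and standardised effect d comes from the noncentral t distribution, with n − 1 degrees of freedom and noncentrality d√n.

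| Effect size | n | Power |
|---|---|---|
| 1.22 | 7 | 76.7% |
| 1.22 | 8 | 84.0% |
| 0.85 | 12 | 76.4% |
| 0.85 | 13 | 80.3% |

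Both stated sizes, 8 and 13, reproduce as the smallest n that reaches 80%. A normal approximation (10.9, so 11) and a one-sided t-test (11) do not give 13, so the two-sided t-test is the calculation that was used. The base figure is sound, but it leaves no slack for losing a completer.

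**Step 2: apply the stated dropout to the stated target.**

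16 × (1 − 0.25) = 12 completers, against 13 required.

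Power at d = 0.85 with 12 completers is 76.4%, which is 3.6 points below 80%. With 12 completers, power reaches 80% only at an effect size of about 0.89 (79.2% at 0.88, 80.1% at 0.89).

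**Step 3: invert the inflation.**

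- Recruits needed: 13 / (1 − 0.25) = 17.33, so 18 per arm. Then 18 × 0.75 = 13.5 expected completers.
- Dropout that 16 recruits can absorb: 1 − 13/16 = 18.75%.

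**Step 4: allow the number of completers to vary.** Assume each participant drops out independently with probability 0.25, so that the number of completers is binomial. Average the power at d = 0.85 over that distribution.

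| Recruited per arm | Expected completers | Chance of at least 13 | Average power |
|---|---|---|---|
| 16 | 12.0 | 40.5% | 75.5% |
| 17 | 12.75 | 57.4% | 78.5% |
| 18 | 13.5 | 71.7% | 81.1% |

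With 16 recruits, the requirement of 13 is more likely to be missed than met.

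**Step 5: check the other arm.** At d = 1.22, 12 completers give 97.0% power. The diet-plus-exercise arm is not affected.

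**The case against.** The best case on the other side is that the discrepancy is small and the figures were never meant to be exact.

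- **Both numbers carry an approximation sign.** Seventeen recruits with four dropouts (4/17 = 23.5%) leave exactly 13. That reading needs the target to move up and the dropout to move down together. At 16 recruits, dropout of 22.5% to 27.5% leaves 12.4 to 11.6 completers. At 17 recruits and 25% dropout, average power is 78.5%. The signs soften the contradiction but do not remove it.
- **The effect size is less certain than the arithmetic.** The 0.85 is a proposed value, set below the 1.22 seen with diet plus exercise. With a full 13 completers, power is 75.4% at an effect size of 0.80 and 84.5% at 0.90. A change of 0.05 in the assumption therefore moves power by slightly more than the dropout error does. This is true and limits the practical weight of the point. It does not make the stated power correct at the stated effect size.
- **Only one arm is affected, and no powered between-arm test suffers.** This also stands. However, the protocol uses the diet-only calculation to size both arms, and no other powered comparison makes up for it.

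**Conclusion.** The concern holds. On the protocol's own inputs, the recruitment target, the dropout rate and the 80% power do not agree. The error is one completer, or two recruits, per arm. It takes power for the diet-only arm from 80.3% to 76.4% at an effect size of 0.85, or to 75.5% on average if dropouts are independent at 25%. The requirement of 13 is right, and only the inflation step is wrong. The diet-plus-exercise arm keeps about 97% power at its assumed effect size of 1.22. The conclusion takes the assumed effect sizes as given and reads 25% as the share of recruits lost, which is the ordinary meaning. The effect on the trial is modest, but the statement is wrong as written and is the protocol's only recruitment target.

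**What to change.** Reword the sentence on dropout in the Sample size section so that its figures agree. Either of the first two options leaves recruitment unchanged:

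1. Keep 16 per arm and 25% dropout, and state that the expected 12 completers give about 76% power at an effect size of 0.85 (80% power at about 0.89).
2. Keep 16 per arm and 80% power, and state that this allows for up to about 19% dropout. This is suitable only if the sponsor can support the lower rate.
3. Keep 25% dropout and 80% power, and recruit 13/0.75 = 17.3, so 18 per arm (36 in total instead of about 32).

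The first two cost one sentence and a slightly less favourable statement of power or tolerated dropout. The third costs four more participants.

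### Can an exploratory comparison of two arms of about 12 to 13 completers be used to size future trials?

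*Protocol*

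**What the plan says.** The Sample size section of the protocol builds the trial on within-arm change. It takes an earlier study that "established an effect size of 1.22 for the change in CRP with dietary energy restriction and vigorous intensity exercise 5 x per week" and finds 8 participants sufficient at that value. It then expects less from diet alone: "an estimated effect size of 0.85 is proposed", for which 13 are "required for a two-tailed paired t-test". Recruitment follows: "Assuming a dropout rate of ~25%, we would aim to recruit ~16 individuals in each intervention arm".

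The contrast between the arms gets one sentence: "Between-group comparisons will be exploratory in nature, to determine sample sizes of future studies comparing the efficacy of the conditions". No between-arm effect, precision target or worthwhile difference is stated, and nothing says which output of the comparison would feed a later calculation.

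The design summary in the opening background, before the heading Systemic biomarkers in Osteoarthritis, describes the exercise component as "using a cycle ergometer to determine the added effects of exercise". That is slightly firmer language than the exploratory status given under Sample size.

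**The concern.** The sentence gives the between-arm comparison a single purpose, planning later trials. The most obvious output of a comparison is an observed difference, and the same paragraph begins its own sizing from an effect observed elsewhere (1.22). A reader could therefore expect the team to put the observed between-arm effect into a sample size formula.

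At this size that would be unwise. Chance would largely set the scale of the next trial: a fortunate difference would give a trial that is too small, and an unfortunate one a trial that looks infeasible. The description of exercise in the background adds to the impression that the difference between arms will be pinned down.

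**Working it through.** **The plan's own figures.** Inputs from the Sample size section: two-sided α 0.05, power 80%, paired t-test, effect sizes 1.22 and 0.85. Exact noncentral-t power gives n = 8 at 1.22 (power 84.0%) and n = 13 at 0.85 (power 80.3%). Both stated figures reproduce.

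**Completers per arm.** 16 × (1 − 0.25) = 12. The plan's own requirement is 13. Both are carried below.

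**Precision of the between-arm difference.** For an unadjusted comparison of changes with equal SDs, in units of the SD of change, the half-width is t(0.975, 2n − 2) × √(2/n):

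- n = 12: 2.074 × 0.4082 = 0.847
- n = 13: 2.064 × 0.3922 = 0.810
- n = 16 (no dropout): 0.722

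**Effect of baseline adjustment.** With one covariate the half-width in residual-SD units is 0.849 (n = 12) or 0.811 (n = 13). Multiplying by √((1 + r)/2) converts to SD of change, assuming equal variances at the two visits. The protocol gives no visit correlation r, so a range is assumed:

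- r = 0.5 (factor 0.866): 0.74 (n = 12), 0.70 (n = 13)
- r = 0.8 (factor 0.949): 0.81 (n = 12), 0.77 (n = 13)

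Adjustment helps somewhat but does not make the estimate precise.

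**What sizing from the observed effect would do.** The protocol states no between-arm difference, so the true values below are illustrations; 0.37 is 1.22 − 0.85 with equal SDs assumed. Required N per arm uses a two-sample t-test, 80% power, two-sided 0.05. The ranges are the N per arm implied by the quartiles of the observed effect (noncentral t), or by the quartiles of the observed variance (chi-square) with the target difference held at the true value.

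| True difference (SD) | N needed | From observed effect, n = 12 | n = 13 | From observed SD, n = 12 | n = 13 |
|---|---|---|---|---|---|
| 0.37 | 116 | 37–1,721 | 39–1,390 | 91–137 | 92–136 |
| 0.5 | 64 | 26–308 | 27–281 | 51–76 | 51–75 |
| 0.8 | 26 | 14–58 | 15–56 | 21–31 | 21–30 |

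At n = 12 the chance of an observed difference at or below zero is 18%, 11% and 2.5% for the three rows.

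**Two cautions on the table.** The SD columns look steady partly because the target difference is fixed at the truth, which removes all uncertainty about the effect from that side. The SD is itself uncertain: its 95% interval multiplies the required N by df/χ²(0.975) to df/χ²(0.025), which is 0.60 to 2.00 at 22 degrees of freedom and 0.61 to 1.94 at 24.

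**What the sentence commits the team to.** The arithmetic condemns one possible use of the comparison. The Sample size section prescribes neither that use nor any other. Taking the SD of change, the visit correlation and the dropout rate from this trial would also serve future sizing, and would be sound.

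**The case for a change.** The strongest case for a change is that the exploratory label limits claims about efficacy but not planning use, which the same sentence prescribes. What it names is the comparison, not an SD, and no worthwhile CRP difference appears anywhere in the protocol. A short rewording would cost almost nothing and close off the poor reading. The precision argument stands in full: nobody should size a trial from an observed effect with an interval of about ±0.8 SD.

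The inference that the team would do so does not stand as firmly. The only precedent in the document cuts both ways. The team did start from an observed 1.22, but it judged that too large for diet alone, lowered it to 0.85 and sized the arms on the lower value, accepting 13 rather than 8. That is some evidence of caution with an observed effect, though 0.85 was still reasoned from 1.22.

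Nor is the rewording quite free. It would have this protocol dictate how a later trial is designed and oblige the team to fix a worthwhile CRP difference now, for which the document offers no basis. Reporting the difference with its interval, and choosing between change scores and baseline adjustment, are ordinary analysis plan content. Replacing the verb in the background description of exercise would be editorial.

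**Conclusion.** No change is needed. An observed between-arm effect from this trial would be too imprecise to size another: the half-width is 0.81 to 0.85 SD of change unadjusted, or about 0.70 to 0.81 with baseline adjustment at assumed correlations of 0.5 to 0.8. All of these figures assume roughly normal changes on the analysis scale, equal SDs and 12 to 13 completers per arm.

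The protocol does not say that this effect will be used. It leaves open which quantity informs future planning, and a competent analyst fills that gap by reporting the difference with its interval and carrying forward the variability estimate. Followed as written, the plan yields valid within-arm results and a between-arm result plainly marked as exploratory. Neither the primary analysis, the recruitment target nor any conclusion of this trial depends on the point. The firmer wording in the background is a small mismatch of tone that the Sample size section already resolves.
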